10.1.11. Publication Policy

- The results of this study may be published or presented at scientific meetings by the Investigator after publication of the overall study results or one year after end of the study (or study termination), whichever comes first.
- The investigator agrees to refer to the primary publication in any subsequent publications such as secondary manuscripts, and to submit all manuscripts or abstracts to the sponsor 30 days before submission. This allows the sponsor to protect proprietary information and to provide comments and the Investigator will, on request, remove any previously undisclosed confidential information before disclosure, except for any study- or Pfizer intervention-related information necessary to the appropriate scientific presentation or understanding of the study results.
- For all publications relating to the study, the Investigator will comply with recognized ethical standards concerning publications and authorship, including those established by the International Committee of Medical Journal Editors.
- The sponsor will comply with the requirements for publication of the overall study results covering all Investigator sites. In accordance with standard editorial and ethical practice, the sponsor will support publication of multicenter studies only in their entirety and not as individual site data. In this case, a coordinating investigator will be designated by mutual agreement.
- Authorship of publications for the overall study results will be determined by mutual agreement and in line with International Committee of Medical Journal Editors authorship requirements.

- If publication is addressed in the clinical study agreement, the publication policy set out in this section will not apply.

10.1.12. Sponsor's Qualified Medical Personnel

The sponsor will designate a medically qualified individual (MQI, also known as the medical monitor) to advise the investigator on study-related medical questions. The contact information for the study medical monitor is documented in the Study Team Contact List located in the Investigator Site File.

Participants are provided with a Pfizer study information card at the time of informed consent which includes contact information for their investigator in case of study-related medical questions. The study information card contains, at a minimum, (a) study number, (b) participant's study identification number, and (c) principal investigator contact information.

10.2. Appendix 2: Clinical Laboratory Tests

Hematology and blood chemistry will be drawn at the time points described in the [SoA](#).

- The tests detailed in [Table 5](#) will be performed by the local laboratory.
- Protocol-specific requirements for inclusion or exclusion of participants are detailed in Section [5](#) of the protocol.
- Additional tests may be performed at any time during the study as determined necessary by the investigator or required by local regulations.
- Pregnancy Testing
 - Refer to Section [5.1](#) Inclusion Criteria for screening pregnancy criteria.
 - Pregnancy testing (urine or serum as required by local regulations) should be conducted at monthly intervals (eg, Day 1 of each cycle) during intervention as per [SoA](#). Following a negative pregnancy test result at screening, appropriate contraception must be commenced, and a second negative pregnancy test result will then be required at the baseline visit on C1D1 before the participant may receive the study treatment. Pregnancy tests will also be done whenever 1 menstrual cycle is missed during the active treatment period (or when potential pregnancy is otherwise suspected) and at the end of the study. If a urine test cannot be confirmed as negative (eg, an ambiguous result), a serum pregnancy test is required. In such cases, the participant must be excluded from participation if the serum pregnancy result is positive.
 - Pregnancy testing (urine or serum as required by local regulations) should be conducted at the end of relevant systemic exposure plus an additional 30 days.
 - At Day 90 and Day 180 after EOT, pregnancy status should be discussed (may be done by telephone, unless the participant is visiting the site for other reasons) and pregnancy test can be conducted as necessary.
 - Additional serum or urine pregnancy tests may be performed, as determined necessary by the investigator or required by local regulation, to establish the absence of pregnancy at any time during the subject's participation in the study.

Table 5. Protocol Specified Laboratory Tests

Hematology	Chemistry	Coagulation	Serology	Urinalysis ^a	Pregnancy Test or Postmenopausal Status
Hematocrit	ALT	INR	HBsAg,		
Hemoglobin	AST	PTT or aPTT ^c	HCV Ab ^d		
	LDH				
Platelets	Alkaline Phosphatase				
WBC	Sodium				
Absolute Neutrophils	Potassium				
Lymphocytes	Magnesium				
Monocytes	Chloride				
Eosinophils	Total Calcium				
Basophils	Total Bilirubin ^b				
	BUN or Urea				
	Creatinine				
	Uric Acid				
	Glucose (non-fasted)				
	Albumin				
	Phosphorous or Phosphate				
	Lipase				
	Amylase				
	Thyroid function test + reflex free T4 and free T3				
	ACTH				
	Cohorts B1 and B2 only: CK (If total CK \geq 3 x ULN, then measure isoenzymes CK-MB and CK-MM)				

ALT = alanine aminotransferase; AST = aspartate aminotransferase; BUN = blood urea nitrogen; CK = creatine kinase; CK-MB = creatine kinase-muscle type, myocardial band; CK-MM = creatine kinase-skeletal muscle; FSH = follicle stimulating hormone; HBsAg = hepatitis B antigen; HCV = hepatitis C virus; INR = international normalized ratio; LDH = lactate dehydrogenase; PTT = partial thromboplastin time; aPTT = activated partial thromboplastin time; T3 = triiodothyronine; T4 = thyroxine; UPCR = urine protein to creatinine ratio

a. Dipstick is acceptable to perform urinalysis. Microscopic analyses if clinically indicated (eg, only after the second positive dipstick result for heme). If $\geq 2+$ protein on urine dipstick, then collect spot urine sample to calculate UPCR or collect 24hr urine.

b. For potential Hy's Law cases, in addition to repeating AST and ALT, laboratory tests should include albumin, creatine kinase, total bilirubin, direct and indirect bilirubin, gamma glutamyl transferase, prothrombin time (PT) or INR, alkaline phosphatase, total bile acids, and acetaminophen drug and/or protein adduct levels.

c. Use either PTT or aPTT consistently at all time points for each participant throughout the course of the study.

d. In the case of apparent ongoing HBV or HCV infection, reflex serum viral load testing will be performed.

Investigators must document their review of each laboratory safety report.

10.3. Appendix 3: Adverse Events: Definitions and Procedures for Recording, Evaluating, Follow-Up, and Reporting

10.3.1. Definition of AE

AE Definition

• An AE is any untoward medical occurrence in a participant or clinical study participant, temporally associated with the use of study treatment, whether or not considered related to the study treatment.• NOTE: An AE can therefore be any unfavorable and unintended sign (including an abnormal laboratory finding), symptom, or disease (new or exacerbated) temporally associated with the use of study treatment.

Events Meeting the AE Definition

• Any abnormal laboratory test results (hematology, clinical chemistry, or urinalysis) or other safety assessments (eg, ECG, radiological scans, vital signs measurements), including those that worsen from baseline, considered clinically significant in the medical and scientific judgment of the investigator. Any abnormal laboratory test results that meet any of the conditions below must be recorded as an AE:
• Is associated with accompanying symptoms.• Requires additional diagnostic testing or medical/surgical intervention.• Leads to a change in study dosing (outside of any protocol-specified dose adjustments) or discontinuation from the study, significant additional concomitant drug treatment, or other therapy.• Exacerbation of a chronic or intermittent preexisting condition including either an increase in frequency and/or intensity of the condition.• New conditions detected or diagnosed after study intervention administration even though it may have been present before the start of the study.• Signs, symptoms, or the clinical sequelae of a suspected drug-drug interaction.• Signs, symptoms, or the clinical sequelae of a suspected overdose of either study intervention or a concomitant medication. Overdose per se will not be reported as an AE/SAE unless it is an intentional overdose taken with possible suicidal/self-harming intent. Such overdoses should be reported regardless of sequelae.• The signs, symptoms, and/or clinical sequelae resulting from lack of efficacy will be reported as an AE or SAE if they fulfill the definition of an AE or SAE and meet the requirements as per Section 8.3.8.1. Also, “lack of efficacy” or “failure of expected pharmacological action” does not constitute an AE or SAE.

Events NOT Meeting the AE Definition

- Any clinically significant abnormal laboratory findings or other abnormal safety assessments which are associated with the underlying disease, unless judged by the investigator to be more severe than expected for the participant's condition.
- The disease/disorder being studied or expected progression, signs, or symptoms of the disease/disorder being studied, unless more severe than expected for the participant's condition.
- Medical or surgical procedure (eg, endoscopy, appendectomy): the condition that leads to the procedure is the AE.
- Situations in which an untoward medical occurrence did not occur (social and/or convenience admission to a hospital).
- Anticipated day-to-day fluctuations of preexisting disease(s) or condition(s) present or detected at the start of the study that do not worsen.
- Worsening of signs and symptoms of the malignancy under study should be recorded as AEs in the appropriate section of the eCRF. Disease progression assessed by measurement of malignant lesions on radiographs or other methods should not be reported as AEs.

10.3.2. Definition of SAE

If an event is not an AE per definition above, then it cannot be an SAE even if serious conditions are met (eg, hospitalization for signs/symptoms of the disease under study, death due to progression of disease).

An SAE is defined as any untoward medical occurrence that, at any dose:

a. Results in death

b. Is life-threatening

The term "life-threatening" in the definition of "serious" refers to an event in which the participant was at risk of death at the time of the event. It does not refer to an event, that hypothetically might have caused death, if it were more severe.

c. Requires inpatient hospitalization or prolongation of existing hospitalization

In general, hospitalization signifies that the participant has been detained (usually involving at least an overnight stay) at the hospital or emergency ward for observation and/or treatment that would not have been appropriate in the physician's office or outpatient setting. Complications that occur during hospitalization are AEs. If a complication prolongs hospitalization or fulfills any other serious criteria, the event is serious. When in doubt as to whether "hospitalization" occurred or was necessary, the AE should be considered serious.

Hospitalization for elective treatment of a preexisting condition that did not worsen from baseline is not considered an AE.

d. Results in persistent disability/incapacity

- The term disability means a substantial disruption of a person's ability to conduct normal life functions.
- This definition is not intended to include experiences of relatively minor medical significance such as uncomplicated headache, nausea, vomiting, diarrhea, influenza, and accidental trauma (eg, sprained ankle) which may interfere with or prevent everyday life functions but do not constitute a substantial disruption.

e. Is a congenital anomaly/birth defect

f. Other situations:

- Medical or scientific judgment should be exercised in deciding whether SAE reporting is appropriate in other situations such as important medical events that may not be immediately life-threatening or result in death or hospitalization but may jeopardize the participant or may require medical or surgical intervention to prevent one of the other outcomes listed in the above definition. These events should usually be considered serious.

Examples of such events include invasive or malignant cancers, intensive treatment in an emergency room or at home for allergic bronchospasm, blood dyscrasias or convulsions that do not result in hospitalization, or development of drug dependency or drug abuse.

- Progression of the malignancy under study (including signs and symptoms of progression) should not be reported as an SAE unless the outcome is fatal within the active collection period. Hospitalization due to signs and symptoms of disease progression should not be reported as an SAE. If the malignancy has a fatal outcome during the study or within the active collection period, then the event leading to death must be recorded as an AE on the eCRF, and as an SAE with CTCAE Grade 5 (see the Assessment of Intensity section).
- Suspected transmission via a Pfizer product of an infectious agent, pathogenic or non-pathogenic, is considered serious. The event may be suspected from clinical symptoms or laboratory findings indicating an infection in a participant exposed to a Pfizer product. The terms "suspected transmission" and "transmission" are considered synonymous. These cases are considered unexpected and handled as serious expedited cases by pharmacovigilance personnel. Such cases are also considered for reporting as product defects, if appropriate.

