8.3.7. Disease-Related Events and/or Disease-Related Outcomes Not Qualifying as AEs or SAEs

Not applicable.

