##### 6.6.1. Adverse events

TEAEs are those events with onset dates occurring during the on-treatment period as defined in [Section 3.5.1](#).

All analyses described will be based on TEAEs (started during the on-treatment period) if not otherwise specified. The AE listings will include all AEs (whether treatment-emergent or not). AEs outside the on-treatment period will be flagged in the listings.

- **Related Adverse Events:** adverse events with relationship to study treatment (as recorded on the AE eCRF page, Relationship with study treatment = Related) reported by the investigator and those of unknown relationship (i.e., no answer to the question 'Relationship with study treatment'). Related AEs are those related to any study drug (i.e., at least one of the study drugs).
- **Serious Adverse Events (SAE):** serious adverse events (as recorded on the AE eCRF page, Serious = Yes).
- **Adverse Events Leading to Interruption of Study Treatment:** adverse events leading to interruption of study treatment (as recorded on the AE eCRF page, Action taken with study treatment = Drug interrupted).
- **Adverse Events Leading to Discontinuation of Study Drug:** adverse events leading to discontinuation of study drug (as recorded on the AE eCRF page, Action taken with study treatment = Drug withdrawn).
- **Adverse Events Leading to Death:** adverse event leading to death (as recorded on the AE eCRF page, Outcome = Fatal, as well as AEs of Grade 5).

- **Immune-related Adverse Events (irAE):** irAEs (as identified according to the methodology outlined in Appendix 1 for a pre-specified search list of MedDRA PTs documented in the Safety Review Plan [SRP] and finalized for analysis of this study's data prior to database lock)
- **Injection site reaction (ISR) related to PF-06801591:** adverse events with relationship to PF-06801591 (as recorded on the AE eCRF page, Relationship with study treatment = Related) reported by the investigator and those of unknown relationship (i.e., no answer to the question 'Relationship with study treatment'), and with high level term (HLT) of Injection site reactions.

Unless otherwise specified, AEs will be summarized by number and percentage of participants with the AE in the category of interest as described above, by treatment arm in Cohort A and by Cohorts B1 and B2, primary SOC, and PT in decreasing frequency based on the frequencies observed for Arm A (for Cohort A) and Cohort B1 (for Cohorts B1 and B2).

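### Protocol Section 10.3.2 says that a death from progression cannot be an SAE and also that it must be recorded as a Grade 5 SAE, and the SAP's fatal and serious TEAE counts inherit the ambiguity

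*Protocol*

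**What the plan says.** **Protocol 10.3.1 (definition of AE).** Among the events that do not meet the AE definition it lists "The disease/disorder being studied or expected progression, signs, or symptoms of the disease/disorder being studied", except where more severe than expected. The same list says that worsening signs and symptoms of the malignancy are to be recorded as AEs, but that progression measured on lesions is not.

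**Protocol 10.3.2 (definition of SAE), opening rule.** "If an event is not an AE per definition above, then it cannot be an SAE even if serious conditions are met". The examples in brackets are "hospitalization for signs/symptoms of the disease under study, death due to progression of disease".

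**Protocol 10.3.2, bullet on progression of the malignancy.** Progression "should not be reported as an SAE unless the outcome is fatal within the active collection period". If the malignancy is fatal, "the event leading to death must be recorded as an AE on the eCRF, and as an SAE with CTCAE Grade 5". This last instruction covers a fatal outcome at any time in the study as well as in the active collection period.

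**Protocol 8.3.7**, headed "Disease-Related Events and/or Disease-Related Outcomes Not Qualifying as AEs or SAEs", is marked as not applicable.

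**Protocol 8.3.1 and the Cohort A follow-up table in Section 1.3.** Active collection runs to at least 90 days after the last dose. In disease and survival follow-up, the table provides for reporting of treatment-related SAEs.

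**SAP 6.6.1.** A fatal AE is an "adverse event leading to death (as recorded on the AE eCRF page, Outcome = Fatal, as well as AEs of Grade 5"). An SAE is any AE marked serious on the same page. Neither definition mentions progression of the disease under study. Both feed by-arm tables of treatment-emergent events in SAP 6.6.1.1 and 6.6.3.

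**The concern.** One section names the same event as its example of what cannot be an SAE and makes it the subject of a mandatory Grade 5 SAE record. An investigator faced with a bladder cancer death can follow the text and either record it on the AE page or leave it off.

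The SAP has no rule that makes the two outcomes equivalent. A progression death recorded as a Grade 5 SAE with treatment-emergent onset counts in three lines of the overall AE summary: TEAEs leading to death, serious TEAEs, and TEAEs of Grade 3 or higher. A progression death not recorded counts in none of them on that account. These are headline safety lines, so a reader should know whether they contain disease outcomes.

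**Working it through.** The plan states no figure to reproduce. The check is a comparison of texts, followed by arithmetic for scale.

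**1. Is the event an SAE?**

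| Place | Death from progression |
|---|---|
| Protocol 10.3.1 | Expected progression is not an AE |
| Protocol 10.3.2, opening rule | Named example of an event that cannot be an SAE |
| Protocol 10.3.2, progression bullet | Must be recorded as an AE and as a Grade 5 SAE |
| Protocol 8.3.7 | Not applicable, so it settles nothing |

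The second and third rows cannot both be followed for the same death.

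**2. Over what period?**

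| Place | Window |
|---|---|
| Protocol 10.3.2, first sentence of the bullet | Fatal in the active collection period (at least 90 days after last dose, Section 8.3.1) |
| Protocol 10.3.2, last sentence of the bullet | Fatal at any time in the study, or in the active collection period |
| Protocol 1.3, Cohort A follow-up | Treatment-related SAEs only, in disease and survival follow-up |

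The study ends 5 years after the last Cohort A randomization (Protocol 4.4). An unrelated progression death in year 4 of follow-up is a mandatory SAE under the second row and outside collection under the first and third.

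**3. What reaches the tables?** A TEAE has onset between first dose and the earlier of last dose plus 30 days and the day before new anti-cancer drug therapy (SAP 3.5.1 and 5.2.7). The test is the onset date, not the date of death. A progression event with onset entered at or before treatment stopped is therefore treatment-emergent even if death came much later. Events with later onset appear only in listings, with a flag.

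**4. Scale.**
- Participants per arm: 1056 / 3 = 352 (1056 randomized, Protocol 4.1.1). The safety set counts treated participants, so the denominator may be slightly smaller.
- One progression death recorded or not recorded: 1 / 352 = 0.28 percentage points of an arm's fatal-TEAE rate. The serious and Grade 3 or higher rates move only if that participant has no other such TEAE.
- The documents do not give the number of progression deaths with onset in the TEAE window. Assumed range of 1 to 10 per arm: 1 / 352 = 0.28 to 10 / 352 = 2.8 points.
- Outer bound: SAP 5.1.2 expects about 64 deaths per two-arm comparison at the EFS final analysis, or 64 / 2 = 32 per arm if split equally. If every one were a progression death with onset in the window, 32 / 352 = 9.1 points. This is not a realistic value, because 64 is an all-cause planning figure and most such deaths would have onset after the window closed.

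**The case against.** The strongest reply is that the opening rule of Section 10.3.2 is general and conditional, while the progression bullet is specific and mandatory, so the specific instruction governs. That is a reasonable reading, and many sites may have adopted it. It does not remove the conflict, because the opening rule uses this very event as its illustration and does not refer to an exception. It also leaves the two windows unreconciled.

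The second reply is that the SAP already shows much of what is needed. Fatal and serious TEAEs are tabulated by system organ class and preferred term, related events are shown separately, and SAP 6.6.2 tabulates reason for death, including disease under study, from a separate death page. This stands in part: a recorded progression death can usually be found by its term. The overall summary lines do not separate it, and no table shows progression deaths that were never entered on the AE page.

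The third reply is that the numbers must be small. High-grade recurrence or progression generally ends study treatment, apart from re-induction after early high-grade Ta recurrence, and the TEAE window closes within 30 days of the last dose. This stands, although the onset-date rule softens it.

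A reader might infer that a control arm with more bladder cancer deaths would be made to look less safe. The documents do not support that. The choice between the two sentences belongs to the site, and nothing shows that it varied by arm within a site. Nor do they show that sites in fact recorded differently from one another.

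**Conclusion.** The contradiction in Protocol 10.3.2 is real, as is the mismatch in time windows. The consequence is minor: the fatal, serious and Grade 3 or higher TEAE counts depend on a recording rule that the protocol does not settle. Each event is worth about 0.28 percentage points, assuming about 352 treated participants per arm. The total is unknown because the documents do not give the number of affected deaths.

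A reader might take the issue to touch the efficacy results. It does not: no EFS, OS or DSS event is taken from the AE page, and the reason-for-death table in SAP 6.6.2 uses its own page. A reader might also treat the 64 expected deaths as the number at risk of misclassification. That figure covers all causes and is not restricted to treatment-emergent onset.

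**What to change.** **Protocol.** Reconcile Sections 10.3.1 and 10.3.2 and the Cohort A follow-up table in Section 1.3 into one rule and one time window for fatal progression. This review does not say which rule is right. Treatment in Cohort A was completed on 16 November 2023 (SAP Section 2), so new wording cannot change how most on-treatment events were recorded. It still matters for follow-up, which runs to 5 years after the last randomization.

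**SAP 6.6.1.1 and 6.6.3.** Show TEAEs leading to death and serious TEAEs by arm, with and without progression of the disease under study, using a list of preferred terms fixed in advance. Cross-check these against deaths with disease under study as the reason in SAP 6.6.2, and report by arm how many of those deaths have a matching fatal AE record and how many do not.

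**Cost.** A wording correction and a repeat of a few safety tables on data already collected. The limitation is that deaths never entered on the AE page can be identified only from the death page, so the cross-check can count them but cannot supply the missing AE record.
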